- 4. Determine for whom the intervention is effective:** This novel CBT intervention for checking (CBT-C) focuses on identifying and challenging maladaptive beliefs about memory, with the aim to increase patients' confidence in their memory for checking situations. In the preliminary treatment investigation, maladaptive beliefs about memory decreased significantly across treatment, and were predictive of decreased checking behaviours at post-treatment (Alcolado & Radomsky, 2016). However, it remains unclear for whom this intervention is most effective. Are all individuals with compulsive checking plagued by maladaptive beliefs about memory, and do patients need to endorse these beliefs in order for this treatment to be effective? These questions will also be examined in this investigation, where the larger sample size will allow for comparisons based on patients' degree of endorsement of maladaptive beliefs about memory.

Hypotheses:

Following directly from the project's objectives, the hypotheses are **(1)** that the treatment (CBT-C) will be effective, in replication of a previous pilot treatment; **(2)** this brief intervention will be more effective than the comparison condition (TAU); **(3)** the effects will be maintained at 6-month follow-

up; and that (4) although the treatment will be effective for all, it will be most effective for those patients with high pre-treatment levels of maladaptive beliefs about memory.

Design/Methodology

Participants:

Participants (N = 50): n = 25 in CBT-C, and n = 25 in TAU; allowing for the testing of an additional 5 participants [predicting an approximate 10% drop-out rate as was seen in the pilot study]) will take part. This sample size is reasonable given the number of OCD referrals our clinic typically receives in a year (approximately N = 50) in conjunction with the active recruitment we will do through the community support groups, allowing for ineligible participants and study attrition. This sample size is also adequately powered for the analyses (see Power Analyses and Statistical Plan, below). Participants will come from one of two sources, either our Anxiety Disorders Clinic or community (see Recruitment, below).

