The novel intervention (CBT-C) to be used is that developed in the pilot study (Alcolado & Radomsky, 2016). This intervention is a manualized 2-session CBT treatment. Agenda elements, including psychoeducation, discussion prompts, and homework exercises are standardized across participants. In the first session, participants are taught about the cognitive theory of checking, the research support behind this theory, and how it may apply to their own checking behaviour. A homework exercise is introduced and practiced to test out this theory. In the second session, the homework results are reviewed. Further education is shared on the nature of memory and the relationship to checking, and a discussion regarding how this applies to the participant's checking then takes place. A second homework exercise is introduced to test this theory. Following each session, patients are also instructed to review a written hand-out of the information presented, as

well as listen to an audio-recording of the session material, in order to enhance their understanding and retention of the material learned between sessions. The hand-out will be emailed or mailed if the participant attends online appointments, whereas they will be provided with a paper copy if meeting in-person.

Treatment as Usual (TAU) during patients' time on our waitlist in our clinic will depend on at what point they have been recruited. It may consist of a 2-session group psychoeducational intervention on anxiety, any medications prescribed by their referring physicians, and/or independent therapy/counseling they may be seeking on the side. TAU for community participants will include any treatments they are currently seeking and will also be tracked during the course of the study. Information about participation in such interventions will be collected during the course of the study (at each assessment visit) in order to accurately characterize participants' TAU in the current study. in order to enhance accurate characterization of TAU.

Procedures:

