Assessments: Eligible participants will undergo informed consent (see Process for Seeking Consent) and participate in a diagnostic interview consisting of the MINI and the Y-BOCS to confirm eligibility. If they are eligible to participate following these diagnostic interviews, they will complete a demographic questionnaire, and will be randomly assigned to receive the new treatment (CBT-C; administered by the principal investigator) or treatment as usual (TAU). The VOCI, OBQ, and DASS questionnaires will be administered at pre- treatment, post-treatment, and at 6-month follow-up. MINI interviews will be audio-recorded for later fidelity coding purposes (i.e., to determine whether different interviewers make the same diagnostic decisions). As previously described, assessment visits may be conducted online using a video conferencing platform such as Zoom, Microsoft Teams, or Doxy or in person at St. Boniface Hospital. In-person visits will only be available once pandemic restrictions are lifted. The questionnaires will be completed online via Qualtrics, a secure University-based online survey software program, for the duration of the pandemic.

Process for Seeking Consent: Participants will complete the consent process at their assessment online or in-person visit, prior to the collection of any data. This will occur following the phone screen to determine initial eligibility and interest. The consent form will be reviewed by the experimenter (either the research assistant or the PI) with the participant and they will have ample opportunity to ask questions. They will be reminded that they can withdraw their consent at any time and cease participation in the study, and that no more data will be collected. The experimenter at this point for any clinic patients will be the study research assistant, and they will remind individuals that their participation is voluntary and will not in any way affect their treatment trajectory or timeline in the clinic so as to minimize any sense of coercion.

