CBT-C: Patients will attend 2, 1-hour individual CBT treatment sessions with a focus on maladaptive beliefs about memory, occurring approximately 1 week apart, whose content is described above. Similar to assessment visits, these sessions will be offered online using a video conferencing platform, or in-person once pandemic restrictions have been lifted. Sessions will be audio-recorded for two reasons. Firstly, as part of participants' homework (as noted above, review of the session content between sessions is required for maximizing understanding and retention). Secondly, a random selection will be reviewed by the research assistant and coded for fidelity to the treatment manual as a treatment fidelity check. Instead of participants providing paper copies of their daily checking activities, homework exercises, and instead of completing paper-based questionnaires at each visit, patients will be directed to fill this information out online, via Qualtrics.

Treatment as Usual (TAU): Patients in the TAU condition from the clinic will remain on the service waiting list and receive the offer of service when it is available. CBT-C has not been part of the OCD service in the past and it will not routinely be offered until the study has been completed and the results have been analyzed.

Debrief: Following the completion of the 6-month follow-up, patients will be fully debriefed as to the full purposes of the study. Regardless of condition assignment, upon completion of treatment, all patient participants who still desire assessment and treatment of their symptoms will remain on our clinic's waitlist for further assessment and treatment recommendations. In line with a stepped care model of treatment, those participants who no longer desire further treatment beyond CBT-C will be

discharged from our clinic. The number of cases for whom this is true will be recorded. For community participants who desire further services following their participation in the TAU condition may receive the active treatment (CBT-C) if interested, and/or, with a family physician referral, they can then access the next appropriate treatment option available in our clinic.

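### Usual care differs by recruitment source, but the plan specifies no stratification by source and has no source term in its model; the order of assignment and baseline questionnaires is also left open

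*Combined protocol and SAP*

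**What the plan says.** The protocol's Participants section states "Participants will come from one of two sources, either our Anxiety Disorders Clinic or community" and sets the size as "Participants (N = 50): n = 25 in CBT-C, and n = 25 in TAU". The expected split between sources is not given.

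Under Interventions, TAU is described once for each source. For clinic patients it depends on when they were recruited, and may include a two-session psychoeducation group, prescribed medication and outside therapy. For the others, "TAU for community participants will include any treatments they are currently seeking". Under Procedures, "Patients in the TAU condition from the clinic will remain on the service waiting list" and are offered service when it comes up. The Debrief paragraph describes community controls as gaining access to clinic services after their participation.

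On allocation, the Assessments paragraph says only that eligible participants "will be randomly assigned to receive the new treatment (CBT-C; administered by the principal investigator) or treatment as usual (TAU"). It gives no sequence, blocking, stratification factor or concealment. That step is listed straight after the demographic form; the VOCI, OBQ and DASS come in the next sentence, as pre-treatment, post-treatment and 6-month measures.

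On consent, "The consent form will be reviewed by the experimenter (either the research assistant or the PI"), with the research assistant doing this for clinic patients.

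The Statistical Plan fits a mixed ANOVA to the VOCI checking subscale, with condition between participants and time within. Source is not in it. Elsewhere the protocol records other treatments and medication at each assessment in case they need controlling for, without a rule for when or how.

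**The concern.** Source is known before assignment and is linked to the care a participant may receive, particularly over the six months to follow-up. A variable of that kind is a natural candidate for stratification and for the model. At 25 per arm its balance is left to chance, and with no source term the analysis cannot absorb any imbalance. At stake are the readability of the one realised comparison and a little precision.

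The second element is timing. The outcome and the hypothesis 4 predictor (BAMI) are both self-report. If a participant knows the arm before completing them, the baseline can be coloured by hope or disappointment, and every change score inherits that. Chance-error arguments do not cover this. The PI is the therapist and may also take consent from community participants, so it matters who releases the assignment and when.

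**Working it through.** **1. The plan's own figure.** The power statement gives N = 44 for two conditions, three time points, a medium effect and high power. Taking f = 0.25, alpha 0.05 and correlation 0.5 (assumed), the condition-by-time test has noncentrality f² × N × 3 / (1 − 0.5) = 0.0625 × 44 × 3 / 0.5 = 16.5 on 2 and 84 df. Power is 0.956, and 44 is the smallest even N that reaches 0.95. N = 50 gives 0.976. The figure reproduces; source plays no part in it.

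**2. Chance of imbalance.** Inputs: 50 participants in 25/25 arms (Participants section) and an assumed community count K. The number of community participants in one arm, x, is hypergeometric, and the difference in share is |2x − K| / 25. Twenty points is therefore a difference of 5 people.

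| Community share | K | P(20 points or more) | P(strictly more than 20) |
|---|---|---|---|
| 20% | 10 | 0.07 | 0.07 |
| 30% | 15 | 0.22 | 0.06 |
| 40% | 20 | 0.15 | 0.15 |
| 50% | 25 | 0.26 | 0.09 |

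When K is odd, a difference of exactly 5 is possible, so the first column is sensitive to the threshold: 7-26% at or above 20 points, 6-15% strictly above. Thirty points or more has probability 0.01-0.04. Simple randomisation gives 0.08-0.20 for 20 points or more.

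**3. What an imbalance does.** Suppose source adds a constant D at every visit and the arms differ by Δp in source share. The arm difference moves by D × Δp at every visit, so the post-minus-pre contrast moves by D × Δp − D × Δp = 0. Only a source effect on change, δ, matters, and its shift is δ × Δp. The documents give no value for δ. The standard error of a two-arm difference, in SD units, is √(2/25) = 0.28.

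| Assumed δ (SD of change) | Shift at 20 points | Shift / SE | Two-sided error given that imbalance |
|---|---|---|---|
| 0.2 | 0.2 × 0.20 = 0.04 | 0.14 | 0.052 |
| 0.5 | 0.5 × 0.20 = 0.10 | 0.35 | 0.064 |
| 0.8 | 0.8 × 0.20 = 0.16 | 0.57 | 0.087 |

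At 30 points the last column becomes 0.055, 0.083 and 0.136.

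**4. Averaged over allocations.** Simulation of a two-arm comparison, N = 50, 40% community, true effect 0.8 SD (assumed):

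| δ | Type I error, unstratified and unadjusted | Type I error, stratified and adjusted | Power, unstratified and unadjusted | Power, stratified and adjusted |
|---|---|---|---|---|
| 0.5 | 0.05 | 0.05 | 0.77 | 0.79 |
| 0.8 | 0.05 | 0.05 | 0.73 | 0.79 |

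Stratifying without adjusting makes the test conservative (error about 0.04 at δ = 0.5 and 0.03-0.04 at δ = 0.8), so the two changes belong together.

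**5. Degrees of freedom.** A source main effect (1 df) acts on the level across visits and leaves condition-by-time unadjusted. Adjusting change needs source-by-time as well, 2 df for three visits: 1 + 2 = 3.

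**6. Order of steps.** The Assessments paragraph runs: interviews, demographic form, assignment; then a sentence on the questionnaires. The Timeline table shows one pre-treatment visit before treatment week 1, which fits questionnaires either before or after assignment. Nothing in the plan settles it.

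**The case against.** A reader might infer that allocation disregards source and that the comparison will be confounded. The documents do not support either reading. The protocol describes no allocation method at all, so all that can be said is that stratification is not specified. Chance imbalance under randomisation is random error, which the test's error rate already covers; step 4 shows average type I error unmoved and a small power gain.

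It is also tempting to say that source determines what the control arm receives. It does so only loosely. Outside treatment appears in both descriptions, and care varies within the clinic group because recruitment may occur at referral, at psychoeducation sessions or after another programme. Usual care is not said to be withheld from CBT-C participants, and the Debrief paragraph keeps clinic patients on the waitlist in either condition. If the effect of CBT-C against usual care differs by source, that is effect modification, which balancing source does not remove.

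The plan does record concurrent treatment and allows for adjustment, and actual treatment is a more direct measure than source. That counts for description. As a covariate it is weaker: the rule is unstated, and treatment taken up after assignment may itself depend on the arm. Source is fixed beforehand.

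These points stand and limit the size of the concern. They do not answer the question of when the baseline is completed. There too, a reader should not conclude that baseline is collected after assignment, or that the PI influences who enters which arm; the text only leaves both possible.

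**Conclusion.** The point holds as a modest gap in specification. Usual care is described differently by source, and source appears in neither the allocation description nor the model. An imbalance of 20 or more points is plausible (about 7-26%; 6-15% strictly above 20). At an assumed 0.5 SD source effect on change it shifts the arm difference by 0.10 SD, about a third of a standard error. The expected gain from stratifying and adjusting is about 0.02 in power, or about 0.06 if the source effect is 0.8 SD. There is no inflation of average type I error and no systematic bias from this route.

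These sizes rest on assumed community shares of 20-50%, assumed source effects and a two-arm simplification of the mixed ANOVA. The baseline-timing gap has no figure attached, but it concerns possible bias and is nearly free to close.

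**What to change.** The budget section says three participants have completed and 47 remain to be recruited, so nearly all of the trial can benefit.

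- **Allocation:** state the method. Use computer-generated blocked lists, one for clinic and one for community.
- **Release:** have existing staff other than the treating PI release each assignment, only after the baseline VOCI and BAMI are complete. Write that order into the Assessments paragraph.
- **Model:** pre-specify source and source-by-time in the VOCI-checking analysis, for all participants including the three already completed.
- **Description:** tabulate usual care received by source and arm, so that any difference in the comparator between sources is visible.

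The cost is slightly more allocation administration and 3 degrees of freedom. No extra participants or visits are needed.

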Inclusion criteria are that participants must be age 18 or older, with a diagnosis of OCD and clinically significant levels of compulsive checking. This is defined as being able to meet the diagnostic criteria for OCD according to the Diagnostic and Statistical Manual of Mental Disorders, 5th Edition (DSM-5; American Psychiatric Association, 2013) based solely on checking symptoms. Other OCD symptoms may be present and checking does not need to be the primary symptom. This study will be offered through online video conferencing platforms or in-person appointments to adhere to pandemic restrictions and maximum safety. If pandemic restrictions are in place, participants must be available for appointments using an online video conference platform such as Zoom, Microsoft Teams, or Doxy.

Exclusion criteria include active suicidality, psychosis, mania, or a substance use disorder that would interfere with participation in the treatment. Participants do not have to be treatment or CBT naïve, and can be medicated, as we are interested in a real-world sample. This information will be collected and tracked in case any differences become relevant for analyses.

Power analyses conducted using G*power (Faul, Erdfelder, Lang, & Buchner, 2007) indicate the sample size of 50 participants will provide more than adequate power to conduct all analyses (see Statistical Plan, below). For the ANOVAs, assuming a medium effect size, 2 conditions, 3 time points, and requiring a high level of power, an N of 44 is needed. For a linear regression with one predictor, with similar effect size and power, N = 43 is needed.

Materials:

Measures: These will include a **background information** form (including age, sex, level of education, marital status, and work status). **The MINI International Neuropsychiatric Interview** (Sheehan et al., 1998) Version 6.0 will be administered to diagnose presence of OCD and any other co-morbid conditions according to the. OCD severity will be assessed using the gold standard **Yale-Brown Obsessive Compulsive Scale** (Y-BOCS; Goodman et al., 1989a). **Validated self-report questionnaires assessing OCD symptoms** (the Vancouver Obsessional Compulsive Inventory [VOCI]; Thordarson et al., 2005), **beliefs** (Obsessive Beliefs Questionnaire [OBQ]; OCCWG, 2005), and associated **affective symptoms** (Depression Anxiety Stress Scale, DASS; Lovibond & Lovibond, 1995) will be administered. To assess beliefs about memory, the new **Beliefs about**

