Memory Inventory (BAMI; Alcolado & Radomsky, 2012) will be administered. The **Memory and Cognitive Confidence Questionnaire** [MAACS; Nedeljkovic & Kyrios, 2007) will also be administered as an additional measure of beliefs about memory. Participants will also be asked about alternative treatments and medication status at each assessment visit in case such differences need to be controlled for, and to accurately characterize the treatment as usual condition (see Treatment As Usual, below). The background information form, VOCI, OBQ, DASS, BAMI, and MACCS will be administered in one of two different ways. If the participant attends online visits, they will complete these measures using a secure online survey through Survey Gizmo. If the participant attends in-person visits once pandemic restrictions are lifted, they will complete these measures on a paper copy of the form. The Y-BOCS and MINI are semi-structured interviews and will be administered by the research assistant.

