Compensation: Participants will be offered \$10 at the end of each assessment visit (for a maximum of \$30 per participant), as a monetary compensation for participants time and efforts, as well as to offset the costs of transportation for their appointments. They will not be offered compensation for their treatment visits. Compensation will be offered in-person, or, if a participant attends online visits, will be provided by mail.

Timeline:

Time point	Phone Screen	Pre-treatment Assessment	Treatment Week 1	Treatment Week 2	Post-treatment Assessment	6-mo. follow-up & debrief
Condition						
A) CBT-C	✓	✓	✓	✓	✓	✓
B) TAU	✓	✓	×	×	✓	✓

✓ = Study visit at this time point

× = No study visit at this time point

Statistical Plan:

Intent-to-treat (ITT) analyses will be conducted in order to accurately depict the progression of all participants through this treatment. As such, if there is drop-out, the last observation point for those participants will be carried forward for all subsequent missing data points of interest. To test **hypotheses 1, 2, and 3** (1 - that the treatment be effective, 2 – as compared to the control group, and 3 – that its effects last over the follow-up period), a mixed-model ANOVA will be conducted. The between-participants independent variable will be treatment condition (CBT-C vs. TAU), and the within-participants independent variable will be time point (pre-treatment, post-treatment, and 6-month follow-up). The dependent variable will be the checking subscale of the VOCI. A similar analysis using average daily time spent checking per week from the daily diaries as a dependent variable, as an alternate measure of checking.

A linear regression will be conducted to test **hypothesis 4** (that the extent to which maladaptive beliefs about memory are endorsed affect outcome). Pre-treatment BAMI total score will be entered as the predictor variable. The criterion variable will be a change score that subtracts pre-treatment VOCI score from post-treatment VOCI score. All analyses will be conducted using SPSS statistical software.

Budget details and available resources:

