Student Research Assistant: \$5510.	
We intend to hire a graduate student (pre-masters level) in clinical psychology for part-time work as a research assistant. Their duties would include assistance with administrative, clinical, and research procedures. More specifically they would aid in managing recruitment, conducting initial phone screens, obtaining informed consent from participants, conducting diagnostic screening interviews (after receiving training and ongoing supervision from the principal investigator), entering data, conducting literature searches, and participating in preparation of the manuscript. It is estimated they would be working approximately 4-5 hours per week on average. (Towards the beginning of the study there would be a greater number of hours worked per week given the intensity of screening and testing, and fewer hours would be worked per week towards the end of the year. Additionally, although some 6-month follow-up assessments may fall outside the funding period, the resources required for follow-up are modest and the PI could administer these if the research assistant is no longer available.)
 
Cost explanation: \$18/hour (plus institutional 19.15% benefits and payroll levy) at 4.94 hours worked per week on average means the total for the year would be \$5510.

The MINI International Neuropsychiatric Interview: \$0.	
The MINI is a validated and well-used semi-structured diagnostic interview used in outcome research. Its fee structure has changed since the time of original budgeting. It is free for use based on the parameters of the current study (they only require projects on a very large scale with large budgets to pay for its use).

Participant Compensation: \$1410 (\$850 from the study sponsor and \$560 from another source)	
All participants will receive \$10 per visit for their assessment visits, of which there are three. Three participants have already completed the study, therefore this is for the remaining 47 participants still to be recruited. Therefore \$1410 is needed in total.
 
After paying for the newspaper advertisement (see below) there will be \$850 left in the budget to devote to this purpose.

	The remaining \$560 necessary to pay all participants will be taken from a start-up grant fund that the PI has recently received that is allowed to be used for miscellaneous research purposes.

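### The CBT-C therapist may run 6-month assessments of a self-reported outcome with no safeguard, and baseline questionnaires are not required before allocation

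*Combined protocol and SAP*

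**What the plan says.** **Outcome.** The Statistical Plan tests hypotheses 1 to 3 with a mixed ANOVA of arm by three time points: "The dependent variable will be the checking subscale of the VOCI". The Measures section lists the VOCI among "Validated self-report questionnaires assessing OCD symptoms". For participants seen online it says that "they will complete these measures using a secure online survey through Survey Gizmo"; in-person visits use paper. The Assessments section names Qualtrics as the platform during the pandemic.

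**Follow-up.** The Assessments section makes the PI the provider of CBT-C. The Student Research Assistant entry in the budget section expects that some 6-month assessments could come after funding ends, and adds that "the resources required for follow-up are modest and the PI could administer these if the research assistant is no longer available".

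**Baseline.** In the Assessments section, consent and the two interviews come first. Of those still eligible it says "they will complete a demographic questionnaire, and will be randomly assigned to receive the new treatment" or TAU. The next sentence reads "The VOCI, OBQ, and DASS questionnaires will be administered at pre- treatment, post-treatment, and at 6-month follow-up". The BAMI is not in that sentence. The Statistical Plan uses its pre-treatment total as the predictor for hypothesis 4, with the pre-to-post change in VOCI as the criterion.

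**The concern.** Participants cannot be blinded to receiving a new therapy rather than waiting, and the outcome is what they say about themselves. Two moments then need protection.

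At 6 months, a CBT-C participant whose visit is run by the PI completes the scale in contact with the person who treated them. TAU participants received no study treatment from the PI. The exposure therefore differs by arm, and it falls on the only visit that bears on hypothesis 3.

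At baseline, a participant who already knows the allocation may answer differently because of it. Baseline VOCI checking is the first level of the time factor, pre-treatment VOCI is subtracted in the hypothesis 4 change score, and baseline BAMI is the predictor there.

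Neither effect could be removed in the analysis, because no unaffected version of the same score would exist.

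**Working it through.** **Follow-up, passages side by side.**
- Assessments: the PI gives CBT-C.
- Timeline: both arms have a 6-month visit, combined with debriefing; only CBT-C has visits in the two treatment weeks.
- Budget: the PI is the fallback for 6-month assessments.
- Recruitment phase and Process for Seeking Consent: for clinic patients, contact and consent go through the research assistant to limit pressure. No matching rule covers outcome collection.

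Taken together, the fallback creates contact with one's own therapist in one arm only. Because the VOCI is self-completed, the route is the participant's response to the therapist's presence, not scoring by the PI.

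**Baseline, passages side by side.**
- Suggesting after allocation: the Assessments section lists interviews, demographic form and random assignment, and mentions the VOCI only afterwards.
- Suggesting before allocation: that VOCI sentence is a schedule for all three time points, and the sentence after it goes back to recording the MINI, so the paragraph is not chronological. The Measures section treats the demographic form and the scales as one set: "The background information form, VOCI, OBQ, DASS, BAMI, and MACCS will be administered in one of two different ways". The Timeline shows a single pre-treatment visit.
- Silent: the Timeline does not place randomisation, and nothing describes concealment or delayed disclosure of the arm.

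Both orders fit the text, so this limb is an omission.

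**Illustration of size (all shifts assumed).** First, the plan's own N = 44 for the ANOVA. With f = 0.25 (my reading of medium), alpha 0.05, correlation ρ = 0.5 between time points, sphericity and power 0.95 (none of these is stated):

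λ = f² × N × m / (1 − ρ) = 0.0625 × 44 × 3 / 0.5 = 16.5, on 2 and 84 df, giving power 0.956.

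N = 44 is reproduced and is not in dispute. At N = 50 the power is 0.976.

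The same model gives the false-positive rate of the group-by-time test when there is no true effect but the arms differ by d at some time point (in SD), with n = 25 per arm:

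λ = (n/2) × Σ(d − mean d)² / (1 − ρ), on 2 and 96 df.

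For 0.3 SD at one time point, Σ = 0.04 + 0.01 + 0.01 = 0.06, so λ = 12.5 × 0.06 / 0.5 = 1.5.

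| Mean arm shift, baseline alone or 6 months alone | λ | Rejection rate |
|---|---|---|
| 0 | 0 | 5% |
| 0.1 SD | 0.17 | 6% |
| 0.2 SD | 0.67 | 10% |
| 0.3 SD | 1.50 | 17% |
| 0.5 SD | 4.17 | 42% |

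At 0.3 SD the rate runs from 14% (ρ = 0.3) to 27% (ρ = 0.7). Simulation with 20,000 runs at ρ = 0.5 gave 5.1% for no shift, 17.3% for 0.3 SD and 41.9% for 0.5 SD.

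These are shifts averaged over a whole arm. If only a third of CBT-C participants fell under the fallback and each shifted by 0.3 SD, the arm mean would move by 0.3 / 3 = 0.1 SD and the rate would be about 6%. The documents give neither the share nor the shift.

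**The case against.** The follow-up provision is conditional budget text: only some visits may be late, and the PI steps in only if the assistant has left. The scale is self-completed, online for online visits, and nothing says that the PI sees answers as they are entered. That reduces the exposure. It does not remove it: no section says that completion is unattended, and paper forms at in-person visits are more exposed.

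On baseline, the harm has no established direction. If hope lowers CBT-C baseline scores, or disappointment raises TAU scores, the apparent benefit of CBT-C shrinks; other reactions would enlarge it. For hypothesis 4, a constant shift within one arm leaves that arm's regression slope unchanged. It matters only if the arms are pooled or the shift varies with BAMI, and the Statistical Plan does not say which arms enter the regression. The 6-month score does not enter that regression at all. These points stand, and they limit the baseline limb to a request for an explicit statement.

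A blanket rule of online-only completion with the PI confined to sending a link would also go too far. It would remove the paper option and leave nobody to debrief participants or ask about other treatments. The fix below avoids this.

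**Conclusion.** The concern holds in a limited form. The follow-up limb rests on a stated provision: the treating PI may run 6-month assessments, without a safeguard, and this creates an exposure specific to CBT-C. The baseline limb is an unclosed gap. Both deserve correction because the remedy is cheap and the analysis cannot repair the damage afterwards. The size and direction of any bias are unknown; the rates above rest on assumed shifts, 25 per arm and no true effect.

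Three stronger readings are tempting but unsupported.
- **Bias from allocation and therapist at both ends.** Opposite 0.3 SD shifts at baseline and 6 months would give a 45% false-positive rate (λ = 12.5 × 0.18 / 0.5 = 4.5). But no therapist influence at baseline is documented, and nothing shows that the two shifts would occur together or in opposite directions.
- **Baseline scales are given after randomisation.** Order of description is not order in time.
- **A designated primary outcome is compromised by a known share of its target effect.** The document labels no outcome primary, and it states only a medium effect, not a difference in SD units.

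**What to change.** 1. Amend the fallback in the budget section, and repeat the rule in the Assessments section: in both arms, whoever runs the visit, post-treatment and 6-month self-reports are completed and submitted unattended through the existing online survey. At in-person paper visits they are completed alone and sealed. Either way this happens before any contact with the PI at that visit. The PI may then debrief and ask about other treatments.
2. State in the Assessments section that all baseline questionnaires (VOCI, OBQ, DASS, BAMI, MACCS) are submitted before the allocation is drawn or disclosed.

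**Cost.** No extra staff and no change to the sample size. Paper visits become slightly less flexible. Unattended completion may leave a little more missing data, which matters here because the Statistical Plan carries the last observation forward: a missing 6-month form after drop-out would be filled with the post-treatment score and look like perfect maintenance. Reminders would limit this. The budget section reports three participants already finished, so the change can reach the other 50 − 3 = 47. If baseline forms already come before allocation, the second statement costs nothing.
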